Surveillance will be used to identify gaps in each of the above components in order that they can be addressed. For example, a particular service line may not be facile at achieving effective decolonization. This would be addressed with patient outreach to that service line. All steps will be determined by a dedicated infection control perioperative team that will use surveillance to guide proactive, evidence-based, plan-do- study-act cycles.

OR PathTrac surveillance procedures: Research assistants will culture the baseline anesthesia environment (adjustable pressure-limiting valve and agent dial of the anesthesia machine) using environmental swabs, anesthesia attending hands on entry to the OR but after an opportunity to wash their hands using the wall-mounted devices using a modified glove juice technique that is simply dipping the dominant hand in a sterile bag containing a sterile, balanced salt solution, the same procedure for resident hands at baseline, the patient nasopharynx, axilla, and inguinal regions following induction of anesthesia and patient stabilization using patient Eswabs as described above, the same provider hand, patient, and environmental cultures at case end, and the patient intravenous stopcock at case end that will be cultured using an environmental swab. All cultures in the OR will be obtained using aseptic practice where the research assistant will be wearing a hat, a mask, and will wash their hands prior to donning gloves. These same procedures will be applied to the patient to follow (the patient undergoing surgery in the same OR after the patient above).

Postoperative Surveillance Cultures: The first patient will be followed to recovery in same day: postanesthesia care unit (PACU), intensive care unit (ICU), hospital floor, or other units. Patients, provider hands, and environmental surfaces will be sampled using the procedures as described above within. A sample proximal to the surgical wound, but outside of the dressing, will be sampled. Patient samples and samples from the patient's recovery room environment will be collected within 48 hours prior to discharge.

Sample Processing: All samples will be sent to RDB Bioinformatics for processing. Results will be entered into the software. The software will guide testing to identify *S. aureus* transmission events. *S. aureus* transmission events will be processed to identify transmission stories, and transmission stories will be reported in the software platform to guide proactive improvements in the bundle.

Infection Tracking: The patient will be followed for 90 days postoperatively to identify and infection. Initial screening criteria will include an elevated white blood cell count, fever ($T > 38$ degrees), anti-infection order, culture, or office documentation of infection. If one or more criteria are present, the patient will undergo a full chart review to determine if they developed a healthcare-associated infection (HAI) as determined by National Healthcare Safety Network (NHSN) definitions. All patient cultures obtained for infectious workup by the usual healthcare teams will be saved by the clinical microbiology laboratory. Samples will be sent to RDB for analysis in order to determine if the organism was clonally-related to an organism isolated from one or more reservoirs during the perioperative period.

Confounding Factor Analysis: Information from the patient medical record will be collected by the study team: date and time of surgery, diagnosis, ASA status (a system for assessing the fitness of patients before surgery), age, comorbidities (the presence of one or more additional diseases or disorders co-occurring with (that is, concomitant or concurrent with) a primary disease or disorder), surgery type and duration, type of anesthesia provided, operating room number, gender, dirty or infected surgery (yes/no), preoperative location, postoperative location, and duration of anesthesia. Data will password protected and kept in microEMR.

All patients will be called at 90 days (Up to 3 attempts will be made) to determine if they developed an infection.

VII.E.7 *Will you attempt to recontact subjects who are lost to follow-up?*

No - those lost to followup will not be recontacted

VII.E.9 *Will subjects be provided any compensation for participating in this study?*

No

VIII. Risks

VIII.1 *What are the risks to subjects including*

- emotional or psychological

- financial

- legal or social

- physical?

Patients: Possible anxiety about properly following instructions on how to decolonize with povidone iodine. There is a rare but possible risk of topical hypersensitivity with topical iodine or chlorhexidine antiseptic solutions.

Providers: None apparent.

VIII.2

What have you done to minimize the risks?

- *If applicable to this study ALSO include:*
 - *How you (members of your research team at Iowa) will monitor the safety of individual subjects.*
 - *Include a description of the availability of medical or psychological resources that subjects might require as a consequence of participating in this research and how referral will occur if necessary (e.g. availability of emergency medical care, psychological counseling, etc.)*

Patients will be consented. Patients will receive thorough instructions for proper use of swab kits, Povidone iodine, and chlorhexidine. The consent process will require confirmation that there are no known allergies to shellfish, Povidone iodine, or chlorhexidine. The rare possibility of a hypersensitivity reaction to the topical Povidone or chlorhexidine antiseptic agents will be communicated. It will be recommended that they call their primary care doctor if they do develop a rash.

Providers will also have an opportunity to decline. Emails will be sent out to providers initially and the day before, and providers will have the opportunity to decline at any point the day of.

VIII.3

Does this study have a plan to have an individual or committee review combined data from all subjects on a periodic basis (such as summary or aggregate safety and/or efficacy data)?

No

IX. Benefits

IX.1

What are the direct benefits to the subject (do not include compensation or hypothesized results)?

None

IX.2

What are the potential benefits to society in terms of knowledge to be gained as a result of this project?

Successful implementation of this study will provide an organized, cost-effective pathway to reduce patient harm for up to 7% of patients undergoing surgery and could be extended hospital-wide to improve quality of care delivered to thousands of patients each year, save the hospital system billions of dollars, and address the issue of antibiotic resistance.

X. Privacy & Confidentiality

X.1

What are you doing to protect the privacy interests of the subjects?

Subjects are consented in a private location. The team member obtaining consent waits until medical personnel have completed their business with the subject and have left the room before beginning the consent procedures.

X.2

Are you collecting the Social Security Number of any subjects for any purpose?

No

X.4

How will information/data be collected and stored for this study (check all that apply):

- Paper/hard copy records (hard copy surveys, questionnaires, case report forms, pictures, etc.) - EPIC lists will remain in EPIC. No PHI will be transferred from UIHC to RDB. Each face sheet of the microEMR (the patient demographic entry sheet) for OR PathTrac and Postoperative observational units will be printed by the research assistant each day, placed into a binder, and the binder

stored in the locked office of the PI. Consents will be maintained in a study binder and stored in the locked office of the PI.

- Electronic records (computer files, electronic databases, etc.) - Preoperative orders will be protected within EPIC. For OR and postoperative surveillance, we will be using the RDB Bioinformatics (University of Iowa Research Park, [name], United States) surveillance system. This system is comprised of an encrypted laptop that contains a micro electronic medical record (EMR) into which patient identification and kit identification numbers are entered as well as surgical clinic testing, ward anesthesia surveillance, and OR PathTrac system modules. The micro EMR and OR PathTrac systems have already undergone beta implementation at Iowa. They are protected by 2-factor authentication and are only accessible to research team members. The clinic and ward surveillance systems will be linked to these systems in the current study. RDB and UIHC have a signed data security plan. It is planned that long term storage of data will be with RDB Bioinformatics at UI Bioventures. This will be discussed in the BAA.
 - Name - [name]
 - Title - Affiliate
 - University Job Classification - PZ01
- Biologic samples (blood draws, check swabs, saliva samples, tissue samples, etc.) - We will use IATA methods for bacterial transport/transfer. Patient swab samples will be stored and identified solely by the kit identification number used to obtain the swab. In the event that a patient subsequently develops an infection, patient cultures will be managed initially by the UIHC clinical lab in accordance with usual care. In addition, samples will later be transferred to RDB Bioinformatics. It is planned that long term storage of biological materials will be with RDB Bioinformatics at UI Bioventures.
 - Name - [name]
 - Title - Associate Professor
 - University Job Classification - FS12

X.5 *Do the confidentiality protections indicated above allow only members of the research team to access the data/specimens?*

No

X.6 *Describe*

RDB Bioinformatics is at UI Bioventures. Bacterial cultures will be de-identified (barcode) and demographic data linked to the barcode. Only bacterial culture data, OR date, surgical duration, OR room and case number, and kit numbers will be shared with RDB.

X.7 *Does your study meet the NIH criteria for a [Certificate of Confidentiality](#) or will you be applying for Certificate of Confidentiality?*

No

XI. Data Analysis

XI.1 *Describe the analysis methods you will use, including, if applicable, the variables you will analyze*

Enrollment/Randomization: Randomization is by the surgical line to treatment or control. The treatment bundle will include the improved RDB Bioinformatics S. aureus decolonization and screening processes described as above, as well as the previously described hand hygiene, environmental cleaning, and vascular care interventions. Active surveillance of bacterial transmission in the perioperative setting for both bundle and usual care groups will be used to drive activities that should further reduce the incidence of bacterial transmission. We will not disrupt processes that are already in place, and results will be entered into the medical record via standard laboratory resulting processes.

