We will be attempting to capture all patients that meet inclusion criteria which could include patients seen and consented in the clinic, seen and consented on the hospital floor, intensive care units (inpatient surgery), or pre-anesthesia testing (PAT). Any patient meeting inclusion criteria that the surgeon obtains surgical consent for could be captured. Poster reminders will be placed in the clinics, on the ward, and PAT. The study consent forms will be attached to the surgical consent forms. Surgical providers obtaining surgical consent will obtain study consent when possible. This will otherwise be executed via our research team via pager. Preoperative kit orders will be completed by surgical providers or physician study team members when needed. The signed and held order will populate a list in EPIC for the PI ([name]) that will be filtered by type of surgery, surgeon, and date of surgery within 10 days. It will include the patient medical record number, address/phone number, and an icon indicating the POC signed and held order. [name] will work the list to send ordered kits to patients. [name] will enter a new signed and held order for the kit and will associate the assigned kit number with the order, which will create a new ICON indicating ordered kit sent to patient. This will also update the Clarity report in EPIC with the kit number in addition to the other previously mentioned fields. The patient will receive the kit along with a reminder for why they received the kit (see attached in miscellaneous), use the kit (up to 3 reminders will be provided by [name] study team), and RDB will receive and process the kits. Patients will use a prepaid mailer to send the kits to RDB which will have the RDB address in the send and return fields so that patients are not revealing their identity to RDB (process okay per USPS). RDB will send returned kit numbers to [name] daily. [name] will complete the signed and held orders for patients in the Clarity report that returned kits for processing. The completed POC will generate another ICON indicating received and processed and will again update the Clarity report. The research assistants will work the list to select 2 patients with completed POC orders, treatment and control, for OR PathTrac Observation each day. The assistants will confirm 1st patient consent. Once confirmed, an OR PathTrac Kit will be ordered in EPIC which creates an ICON indicating consent confirmed, a consent confirmed box checked in the RDB microEMR will be placed (3 ways for tracking consents, the written document and two electronic confirmations), and the preoperative swab and OR PathTrac kit numbers entered into the microEMR along with baseline patient demographic information (OR room number and case number, surgery duration, date and time). Informed, written consent will be obtained from the second patient on the day of surgery (see attached consent for patient 2), an OR PathTrac Kit ordered, demographic information (see previous) entered into the microEMR, and surveillance completed. If the second patient does not provide consent for their samples, the pair will be excluded and recruitment continued to reach 1,000 pairs. Our prior experience and recent experience at the University of Iowa strongly suggests that patient refusal to provide written consent for intraoperative cultures will be a rare event. The assistant will then follow the 1st patient to the recovery area for sampling as previously described using the Ward Environment Surveillance (WES) kits. The WES kit number will be associated by the micro EMR to the other kit units. This

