- Other - The attached poster which summarizes elements of the study consent will be made available as a visual aide/reminder for both the surgical team and the patients.
 - Consent Document

- VII.D.16** ***Are you requesting a waiver of documentation of consent (either no subject signature or no written document)?***
Yes

- VII.D.17** ***Choose one of the following to indicate why you are requesting that the IRB waive the requirement to obtain a subject signature as documentation of consent:***
- A.** The research presents no more than minimal risk (minimal risk means the probability and magnitude of harm or discomfort anticipated in the research are not greater in and of themselves than those ordinarily encountered in daily life or during the performance of routine physical or psychological examinations or tests)

AND

The study involves no procedures for which consent is normally required outside of a research context. *(This type of waiver is often permitted for a minimal risk mail-out survey that includes a cover letter with all elements of consent, and returning the survey indicates consent. You cannot request this waiver if the study also involves the use of any protected health information (PHI).)*

- VII.D.18** ***Explain why this meets the chosen criteria in A. or B. above:***
This applies only to the clinician subjects, and, this is minimal risk. We are not collecting provider identifiers. All bacteria collected from providers will receive a unique barcode that will not be linked to the specific provider, only to the type of provider (anesthesia attending or anesthesia assistant).

- VII.D.19** ***Before the subject gives consent to participate are there any screening questions that you need to directly ask the potential subject to determine eligibility for the study?***
Yes

- VII.D.20** ***List any screening questions you will directly ask the potential subject to determine eligibility.***
Are you allergic to iodine, shellfish, or chlorhexidine? If the answer is yes, they will not be enrolled

- VII.D.21** ***Will you keep a screening log or other record that would include information on people who do not enroll in the study?***
Yes

- VII.D.22** ***Describe the information being collected and the purpose for keeping this information.***
For each service line, we will collect age and sex for those patients so that we can assess for biases, such as selection bias.

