We will also track patients who did not send the kits in (via EPIC reports). These patients will not undergo surveillance because they will not have

completed the required screening component. If three calls are made and they do not use the kits, they will be considered lost to f/u. This will be important information when results are reported.

VII.D.23 *Will this information be shared with anyone outside the UI research team members?*
No

VII.D.25 *After the subject agrees to participate (signs consent), are there any screening procedures, tests, or studies that need to be done to determine if the subject is eligible to continue participating?*
Yes

VII.D.26 *List and describe screening*
As described in VII.D.22, the patient must use and return the preoperative swab kits. Three reminders will be provided. If they do not complete the initial screening process, they will be considered lost to f/u. Information required to meet inclusion criteria will be self evident (age which is in the chart, surgical service line which is already known...they are in the randomized line, and need for general/regional anesthesia (this is decided by the procedure).

VII.D.27 *Discuss how much time a potential subject will have to agree to consider participation and whether or not they will be able to discuss the study with family/friends before deciding on participation.*
The patient will be seen in clinic, PAT, or on the floor/ICU as part of their visit. The initial time to decide will be limited by the study visit, as a preoperative order must be placed. However, they will be able to decline at any point down the road as previously described, including simply deciding not to use and return the ordered kit.

VII.D.28 *How long after the subject agrees to participate do study procedures begin?*
Our goal is to focus on a 10-day window prior to surgery so that the kit can be shipped (two days), received (two days), processed (up to 2 days), and in the treatment group, treated for 2-4 days.

VII.D.29 *Provide a description of the enrollment and consent process for adult subjects*

- *Describe each study population separately including control population*
- *Include when recruitment and consent materials are used*

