Reducing Perioperative S. aureus Transmission via use of an Evidence-Based, Multimodal Program Driven by an Innovative Software Platform (OR PathTrac)

9/20/2018

Statistical Analysis

Multiple statistical methods were used. For simplification, we list the statistical methods in the precise sequence they are reported in the results.

The Fisher exact test was used to compare patient and procedural demographic information for treatment vs control groups and for cases involving *S* aureus transmission. Similarly, the distribution of patients by ASA scores greater than 2 and by sex for enrolled vs eligible patients were compared by surgeon using the Mantel-Haenszel test.

The Fisher exact test was also used to examine the potential association of each of the covariates mentioned earlier with *S aureus* transmission. None were associated.

A 2-sided Wilcoxon-Mann-Whitney test was used to examine the association of treatment assignment with the number of transmitted *S aureus* isolates. Poisson regression was used to estimate the incidence risk ratio (IRR) of *S aureus* transmission for the independent variable of treatment. Poisson regression was used to estimate the IRR because the incidence of transmission was so large (ie, much greater than 10%) that the odds ratio estimated using logistic regression would be a biased estimator of the relative risk.²⁴ We repeated the analysis using multilevel Poisson regression clustering by surgeon or specialty.

The Fisher exact test was used to compare the proportion of patients in the treatment group with transmission events before vs after surveillance feedback and the proportion of patients with SSI with and without documented *S aureus* transmission. Poisson regression was used to compare the proportion of patients with SSI with and without documented *S aureus* transmission, clustered by surgeon.

The proportion of patients with SSIs was compared with the Fisher exact test. Time to infection was evaluated by Cox proportional hazard modeling. We repeated the analysis using multilevel Poisson regression clustering by surgeon and specialty.

There were no missing data for the primary and secondary outcomes. Calculations were performed using Stata version 16.1 (StataCorp). All P values were 2-sided, and P < .05 was taken to indicate statistical significance.

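### The SAP's enrolled-versus-eligible check uses ASA class and surgeon, which have no documented source for patients not enrolled, and with no split by arm it is weak against opposite selection in the two arms

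*Protocol*

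**What the plan says.** **Records on people not enrolled.** Protocol VII.D.22 describes the log: "For each service line, we will collect age and sex for those patients so that we can assess for biases, such as selection bias". The same answer adds that unreturned kits are tracked through EPIC reports. The data elements used to find candidates (VII.D.2) are age, surgical clinic visit and allergies.

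**ASA and surgeon.** ASA status appears under Confounding Factor Analysis in VII.E.6: "Information from the patient medical record will be collected by the study team: date and time of surgery, diagnosis, ASA status". That paragraph follows the post-consent procedures and does not say whether it covers eligible patients who did not enroll. Surgeon appears in VI.15 and VII.D.29 as a filter on the EPIC list of patients with a kit order. It is not listed as a log field.

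**The check.** The SAP states that "ASA scores greater than 2 and by sex for enrolled vs eligible patients were compared by surgeon using the Mantel-Haenszel test". It mentions neither age nor arm in this sentence, and no test of homogeneity or interaction. The sentence before it plans a separate comparison: "The Fisher exact test was used to compare patient and procedural demographic information for treatment vs control groups".

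**Consent and allocation.** The service line is the unit of randomization (VI.13). On consent, VI.15 says: "Surgical providers obtaining surgical consent will obtain study consent when possible". VII.D.26 treats the patient's randomized line as already known at screening, and VII.D.29 has treatment or control kits sent according to the line.

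**The concern.** When whole service lines are randomized and patients are consented afterwards, those seeking consent can know the arm. Patients approached or agreeing in bundle lines may then differ from those in usual-care lines. Selection that is the same in both arms mainly limits generalizability. Selection that differs by arm biases the comparison of arms. A comparison of enrolled with eligible patients is the right kind of check, but two features of this one looked wrong.

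- The variables tested are not those logged. A reader cannot tell where ASA class and surgeon come from for the eligible patients who did not enroll, or whether they cover all of them.
- A Mantel-Haenszel test over all surgeons estimates one common odds ratio. If each surgeon works in one arm, opposite selection in the two arms offsets in that estimate, and a null result could be read as evidence against differential selection.

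**Working it through.** **Step 1. Fields set side by side.**

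| Variable | Logged for people not enrolled (Protocol VII.D.22) | In the SAP's enrolled-versus-eligible check |
|---|---|---|
| Age | yes | no |
| Sex | yes | yes |
| ASA above 2 | not listed | yes |
| Surgeon | not listed (log is by service line) | yes, as stratum |

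Only sex is common to both, and even for sex the stratum differs: service line in the log, surgeon in the SAP.

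**Step 2. Inputs for an illustration.** The plan gives no figure for this check, so there is none to reproduce. From the documents: 500 enrolled first patients per arm (XI.1) and a two-sided 0.05 level (SAP). Assumed: 20 surgeons per arm, each working in one arm only; 25 enrolled (20 × 25 = 500) and 100 eligible but not enrolled per surgeon; ASA above 2 in 40% of those not enrolled.

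**Step 3. Formulas.** Each surgeon's table has a, b = enrolled with and without ASA above 2; c, d = not enrolled with and without; n = 125.

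- Common odds ratio (OR) = Σ(ad/n) / Σ(bc/n)
- Chi-squared = [Σ(a − E)]² / ΣV, with E = (a+b)(a+c)/n and V = (a+b)(c+d)(a+c)(b+d) / [n²(n−1)]

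**Step 4. Equal and opposite selection** (35% of enrolled in bundle, 45% in usual care, expected counts).

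- Bundle: a = 8.75, b = 16.25, c = 40, d = 60. OR = 525/650 = 0.81. Σ(a − E) = 20 × (8.75 − 9.75) = −20 and ΣV = 95.93. Chi-squared = 400/95.93 = 4.17, p = 0.04.
- Usual care: a = 11.25, b = 13.75, c = 40, d = 60. OR = 675/550 = 1.23. Σ(a − E) = +20 and ΣV = 97.54. Chi-squared = 400/97.54 = 4.10, p = 0.04.
- Both arms together: OR = (525 + 675)/(650 + 550) = 1.00. Σ(a − E) = −20 + 20 = 0. Chi-squared = 0, p = 1.0.

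**Step 5. Other patterns, same set-up.**

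- One arm only (30% bundle, 40% usual care): OR = (450 + 600)/(700 + 600) = 0.81. Chi-squared = (−40)²/(95.00 + 96.77) = 8.34, p = 0.004. Detected.
- Opposite but unequal (30% bundle, 45% usual care): OR = (450 + 675)/(700 + 550) = 0.90. Chi-squared = (−40 + 20)²/(95.00 + 97.54) = 2.08, p = 0.15. Weakened.

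**Step 6. Sensitivity.** Simulation, 2,000 trials per row, with 10 surgeons per arm and ASA above 2 in 50% of eligible patients (both assumed). The 6,000 eligible per arm is 1,200 per line (VI.14) times 5 lines. Shifts are in percentage points among the enrolled.

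| Shift, bundle / usual care | Pooled test rejects | Bundle-arm test rejects | Usual-care-arm test rejects |
|---|---|---|---|
| −10 / +10 | 4% | >99% | >99% |
| −5 / +5 | 5% | 65% | 66% |
| −10 / +5 | 36% | >99% | 66% |
| −10 / 0 | 92% | >99% | 5% (no selection in this arm) |

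In expected-count tables, equal and opposite shifts also cancelled exactly at 3,000 and 1,000 eligible per arm and at 30% ASA above 2. With the unequal −10/+5 shift and only 1,000 eligible per arm, the pooled test did reach significance (p = 0.03 at 50%, 0.02 at 30%).

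**Step 7. What a between-arm test gives in the Step 4 case.** The ratio of odds ratios is 1.227/0.808 = 1.52, with natural log 0.418. Summing over surgeons, the cells are 175, 325, 800, 1,200 and 225, 275, 800, 1,200. The sums of reciprocals are 0.01087 and 0.01016. So z = 0.418/√0.02104 = 2.88, p = 0.004.

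**The case against.** - **The SAP also compares the arms directly.** In the Step 4 case, 175/500 versus 225/500 gives a Fisher p of 0.0015. If ASA is among the characteristics compared, the imbalance would be seen. XI.2 of the protocol also plans a balance check on other variables. So a reader should not infer that the enrolled-versus-eligible test is the only safeguard, or that the plan as a whole would hide the problem. What remains is interpretation: with at most 10 lines randomized, arms can differ in ASA through case mix alone, and the Fisher test cannot tell that from selection.
- **The data may be obtainable.** One might infer that the ASA comparison cannot be done. The documents do not support that. ASA and surgeon could be drawn from EPIC, surgeon is already on the list of patients with kit orders, and the SAP reports the comparison in the past tense. What is missing is a documented source.
- **Pooling is read from silence.** The sentence opens by likening itself to a treatment-versus-control comparison, so a split by arm may have been meant. None is written. That each surgeon works in one arm is likewise an assumption.
- **Blindness is the extreme case.** To call the test blind to differential selection would go too far. Exact cancellation needs equal and opposite shifts. One-sided selection was found in 92% of simulated trials, and selection in the same direction in both arms is found too.
- **The log is kept by service line, hence by arm.** That is true, and it would allow age and sex to be compared within arms. The SAP's check does not use it that way.

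**Conclusion.** The point holds as a cheap improvement to a secondary check. The mismatch rests on the text alone: ASA class and surgeon have no documented source for eligible patients who did not enroll, and age is logged to assess selection bias but left out of the enrolled-versus-eligible check. The statistical part rests on reading the Mantel-Haenszel test as written, without a split by arm, and on surgeons working mostly within one arm. Under those conditions opposite selection is attenuated (36% rejection at −10/+5 points, against >99% and 66% within arms) and vanishes when equal and opposite. These sizes depend on assumed surgeon numbers, ASA prevalence and eligible counts. Nothing in the documents shows that selection occurred or that the primary estimate is biased. A null pooled result would simply be weak evidence against selection that runs in opposite directions in the two arms.

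**What to change.** 1. **Data source.** Add ASA class and surgeon for eligible patients who did not enroll to the screening log, or name the EPIC source from which they are drawn. Align the wording of VII.D.22 and the IRB description with it. If the comparison has already been run, state the source used and how complete it was.
2. **SAP.** Compare enrolled with eligible-but-not-enrolled patients on age, sex and ASA above 2 separately within each arm, keeping the surgeon strata. Then test whether the odds ratio differs between arms (an arm-by-enrollment interaction). Report the arm-specific odds ratios with confidence intervals whatever the p-values.

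The cost is a few extra chart fields, the matching IRB wording and one more descriptive analysis. The primary analysis and the conduct of care are unaffected.
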